### 2.2.2.2 Ongoing studies

The following studies of bimekizumab are ongoing:

- PS0014 is a Phase 3, long-term extension study for eligible subjects from the Phase 3 PSO feeder studies to assess the safety, tolerability, and efficacy of bimekizumab.
  - DV0002 and DV0006 are multicenter, randomized, open-label studies to evaluate the safe and effective use of the prefilled safety syringe or the auto-injector for the sc self-injection of bimekizumab solution by subjects with moderate to severe PSO. DV0002 and DV0006 are substudies of PS0014; DV0002 is being conducted in North America, and DV0006 is being conducted in the EU and Japan.
- PS0015 is a Phase 3b, randomized, double-blind, secukinumab-controlled, parallel-group study to evaluate the efficacy and safety of bimekizumab administered sc to subjects with moderate to severe chronic plaque PSO.
- PA0009 is a Phase 2b, long-term extension study for eligible subjects from PA0008 to assess the safety, tolerability, and efficacy of bimekizumab.
- PA0011 is a Phase 3, multicenter, randomized, double-blind, placebo-controlled study evaluating the efficacy and safety of bimekizumab in the treatment of subjects with active PsA.
- PA0012 is a Phase 3, multicenter, OLE study to assess the long-term safety, tolerability, and efficacy of bimekizumab in the treatment of subjects with active PsA who complete PA0010 or PA0011.
  - DV0004 is a multicenter, randomized, open-label study to evaluate the safe and effective use of the prefilled safety syringe or auto-injector for the sc self-injection of bimekizumab solution by subjects with active PsA. DV0004 is a substudy of PA0012.
- AS0009 is a Phase 2b, long-term extension study for eligible subjects from AS0008 to assess the safety, tolerability, and efficacy of bimekizumab.
- AS0010 is a Phase 3, multicenter, randomized, double-blind, placebo-controlled study evaluating the efficacy and safety of bimekizumab in subjects with active nonradiographic axial spondyloarthritis.
- AS0011 is a Phase 3, multicenter, randomized, double-blind, placebo-controlled study evaluating the efficacy and safety of bimekizumab in subjects with active AS.

---

- AS0014 is a Phase 3, multicenter, OLE study to assess the long-term safety, tolerability, and efficacy of bimekizumab in the treatment of subjects who complete AS0010 or AS0011.
- AS0013 is a Phase 2a, active-controlled study evaluating the efficacy and safety of bimekizumab compared with CZP in subjects with active AS.
- HS0003 and HS0004 are Phase 3, multicenter, randomized, double-blind, placebo-controlled studies evaluating the efficacy and safety of bimekizumab in subjects with moderate to severe HS.
- HS0005 is a Phase 3, multicenter, OLE study to assess the long-term safety, tolerability, and efficacy of bimekizumab in the treatment of subjects who complete HS0003 or HS0004.

Additional information on the clinical data for bimekizumab is available in the current version of the IB.

## **2.3 Adalimumab**

In this study, the efficacy of bimekizumab will be assessed with reference to the active-reference drug, adalimumab. Adalimumab's mechanism of action occurs through TNF $\alpha$  inhibition compared with bimekizumab's inhibition of IL-17A and IL-17F (HUMIRA $^{\circledR}$ , 2016).

Adalimumab has been approved for the treatment of several auto-immune diseases such as PsA, RA, AS, Crohn's disease, HS, and plaque PSO in the US and EU, as well as in many other countries globally, and is among the first line standard of care biologic therapy for patients not responding to conventional disease-modifying antirheumatic drugs (cDMARDs).

## **3 STUDY OBJECTIVES**

### **3.1 Primary objective**

The primary objective is to demonstrate the clinical efficacy of bimekizumab administered sc Q4W for 16 weeks compared with placebo in the treatment of subjects with active PsA, as assessed by the ACR50 response.

### **3.2 Secondary objectives**

The secondary objectives of the study are as follows:

- To assess the efficacy of bimekizumab compared with placebo
- To assess the safety and tolerability of bimekizumab
- To assess the impact of bimekizumab on patient-reported quality of life
- To assess the impact of bimekizumab on skin PSO in the subgroup of affected subjects at Baseline
- To assess the impact of bimekizumab on functional improvement
- To assess the impact of bimekizumab on radiographic changes in the hands and feet
- To assess the impact of bimekizumab on extra-articular disease manifestations (dactylitis, enthesitis)

### **3.3 Other objectives**

Other objectives are as follows:

- To descriptively assess the efficacy of bimekizumab with reference to adalimumab
- To assess the immunogenicity of bimekizumab
- To assess the impact of bimekizumab treatment on axial disease
- To assess the maintenance of treatment effect
- To assess nail PSO in the subgroup of affected subjects at Baseline
- To explore the exposure response relationship of bimekizumab
- To assess the effect of bimekizumab on gene and protein expression, and explore the relationship between genomic, genetic, and proteomic biomarkers and disease biology, drug treatment and inflammatory and immune responses (from consenting subjects who agree to participate in the biomarker substudy)
- To assess the impact of bimekizumab on social life and work productivity

## **4 STUDY VARIABLES**

### **4.1 Efficacy variables**

#### **4.1.1 Primary efficacy variable**

The primary efficacy variable for this study is the ACR50 response at Week 16.

### **4.2 Secondary variables**

#### **4.2.1 Secondary efficacy variables**

The secondary efficacy variables for this study are as follows:

- Change from Baseline in Health Assessment Questionnaire—Disability Index (HAQ-DI) at Week 16
- PASI90 response at Week 4 and Week 16 in the subgroup of subjects with PSO involving at least 3% BSA at Baseline
- Change from Baseline in the Short Form 36-item Health Survey (SF-36) Physical Component Summary (PCS) at Week 16
- Minimal Disease Activity (MDA) response at Week 16
- Change from Baseline in Van der Heijde modified Total Sharp Score (vdHmTSS) in subjects with elevated hs-CRP and/or at least 1 bone erosion at Baseline at Week 16
- Enthesitis-free state in the Leeds Enthesitis Index (LEI) at Week 16 in the subgroup of subjects with enthesitis at Baseline in the pooled population of PA0010 and PA0011
- Dactylitis-free state based on the Leeds Dactylitis Index (LDI) at Week 16 in the subgroup of subjects with dactylitis at Baseline in the pooled population of PA0010 and PA0011
- Change from Baseline in vdHmTSS in the overall population at Week 16

- ACR20 response at Week 16
- ACR70 response at Week 16
- Proportion of subjects with an Investigator Global Assessment (IGA) score of 0 (clear) or 1 (almost clear) AND at least a 2-grade reduction from Baseline at Week 4 and Week 16 in the subset of subjects with psoriatic skin lesions at Baseline
- Change from Baseline in the Patient's Assessment of Arthritis Pain (PtAAP) at Week 16
- Enthesitis-free state based on the Spondyloarthritis Research Consortium of Canada (SPARCC) index at Week 16 in the subgroup of subjects with enthesitis at Baseline
- Change from Baseline in Psoriatic Arthritis Impact of Disease-12 (PsAID-12) total score at Week 16

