## 9.14 Leeds Enthesitis Index (LEI)

Enthesitis, the inflammation at the bone insertion of tendon, ligament, or joint capsule, is common in PsA. The LEI is a new enthesitis index designed for use in PsA (Healy and Helliwell, 2007) adopted for use in randomized controlled studies involving subjects with PsA. Enthesitis will be assessed by palpation on the lateral epicondyles of the humerus (elbows), medial femoral epicondyles (knees), and Achilles tendons (heels) bilaterally and scored as 0=no pain and 1=painful.

---

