Missing data at Week 16 that are not preceded by an intercurrent event, and any data after an intercurrent event will be imputed as non-responders.

The statistical hypothesis for the ACR50 response at Week 16 is that the conditional odds ratio for ACR50 response in the bimekizumab treatment compared with placebo treatment is equal to 1.

A logistic regression model will be used to assess the treatment effect on ACR50 response at Week 16. The model will include a fixed effect for treatment. The suitability of including the randomization stratification variables, region and bone erosion at Baseline will be assessed and will be added to the model if appropriate. Comparisons will be made using the 2-sided Wald test at a significance level of  $\alpha=0.05$  (ie,  $H_1$  in [Figure 14-1](#)). The odds ratio versus placebo, p-value, and the 95% CI will be calculated.

---

Any use of prohibited or rescue medications through Week 16 would constitute an important protocol deviation which would be accounted for when the sensitivity analysis based on the PPS is performed (see [Section 14.3.1.1.1](#)).

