#### **14.3.1.2    Analysis of the secondary efficacy variables**

The secondary efficacy variables will be analyzed for all subjects in the RS.

All binary variables that are part of the testing hierarchy are given below:

- PASI90 responders at Week 16 will be analyzed to evaluate the composite estimand. The composite estimand combines the clinically meaningful improvement from Baseline in PASI90 response and not discontinuing treatment early.
- The proportion of subjects achieving MDA status at Week 16 will be analyzed to evaluate the composite estimand. The composite estimand combines (1) achieving the MDA status with (2) not discontinuing treatment early.
- The proportion of subjects with enthesitis at Baseline achieving enthesitis-free status at Week 16 will be analyzed to evaluate the composite estimand. The composite estimand combines (1) achieving the enthesitis-free status with (2) not discontinuing treatment early. For this analysis, the PA0010 and PA0011 data will be pooled.

---

- The proportion of subjects with dactylitis at Baseline achieving dactylitis-free status at Week 16 will be analyzed to evaluate the composite estimand. The composite estimand combines (1) achieving the dactylitis-free status with (2) not discontinuing treatment early. For this analysis, the PA0010 and PA0011 data will be pooled.

The statistical hypothesis for the binary variables at Week 16 is that the conditional odds ratio for binary variables in the bimekizumab treatment compared with placebo treatment groups is equal to 1.

The binary variables will be analyzed using the same analysis methods and estimand approach as used for the primary variable ([Section 14.3.1.1](#)).

If appropriate ie, where the outcome variable (eg, PASI90 response) is an assessment of skin/dermatological manifestations of PsA the fitted model will exclude the fixed term bone erosion at Baseline.

All continuous variables that are part of the testing hierarchy are given below:

- Change from Baseline in HAQ-DI at Week 16
- Change from Baseline in the SF-36 PCS score at Week 16
- Change from Baseline in vdHmTSS at Week 16

Continuous variables will be analyzed to evaluate the hypothetical estimand as defined below:

1. Population = Subjects enrolled according to the protocol-specified inclusion/exclusion criteria and randomized to IMP.
2. Subject level outcome = variable as stated in [Section 4.2.1](#)

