## **14.9 Determination of sample size**

Approximately 840 subjects will be randomly assigned in a 3:2:1 ratio to the following treatment groups: bimekizumab 160mg sc Q4W (420 subjects), placebo (280 subjects), adalimumab 40mg sc Q2W (140 subjects).

The primary efficacy analysis is based on the bimekizumab dose versus placebo for ACR50 response at Week 16. It is planned that only descriptive summaries will be provided for the adalimumab reference arm. No statistical comparisons will be made between adalimumab and the other treatment groups.

All sample size and power calculations were done at a significance level of 0.05.

All sample size and power calculations were performed using the software nQuery Advisor® 7.0.

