### **14.9.2 Power calculations for secondary endpoints**

The assumptions for power calculations of the secondary endpoints included in the hierarchy, and for which supporting data exists, are based on the interim results of the Phase 2b

---

bimekizumab study PA0008 and the FUTURE 1, FUTURE 2, FUTURE 5, and SPIRIT P1 studies. All power calculations for binary endpoints were performed using a 2-sided 2-sample Chi-square test with continuity correction (Fleiss et al, 1980). All power calculations for continuous endpoints were performed using a 2-sided 2-group Satterthwaite t-test (Moser et al, 1989).

For the PASI90 response at Week 16, the bimekizumab 160mg Q4W treatment response at Week 12 is 45% (n=20) in the TNF $\alpha$ -naïve population of PA0008 at Week 12 and 46% (n=28) at Week 12 in the mixed TNF $\alpha$  exposure population. The placebo PASI90 response at Week 16 is based on the subgroup analyses of TNF $\alpha$  therapy-naïve subjects in PA0008 (9.1% at Week 12; n=22), FUTURE 2 study (9.7% at Week 24; n=63), and SPIRIT P1 study (1.5% at Week 12; n=67). Therefore, a placebo PASI90 response rate of 10% is assumed. With those assumptions, the study has >99% power to detect a true treatment difference at an assumed 60% of subjects with BSA  $\geq$ 3% of the planned sample size.

For change from Baseline in HAQ-DI at Week 16, the between treatment differences of the change from Baseline in HAQ-DI of in the mixed TNF $\alpha$  exposure population of the PA0008 at Week 12 were used. The bimekizumab 160mg Q4W treatment group mean change from Baseline in HAQ-DI at Week 12 of -0.37, SD=0.47 (n=41) versus placebo mean change from Baseline in HAQ-DI at Week 12 of -0.13, SD=0.50 (n=42). With those assumptions, the study has >99% power to detect a true treatment difference of -0.24 at the planned sample size.

For change from Baseline in PCS of SF-36 at Week 16, the between treatment differences of the change from Baseline in PCS of SF-36 of the TNF $\alpha$ -naïve population of FUTURE 2 study (Kavanaugh et al, 2016) at Week 24 were used. The bimekizumab 160mg Q4W treatment group assumes the secukinumab 150mg treatment group mean change from Baseline in SF-36 PCS at Week 24 of 7.91, SD 7.38 (N=63) versus placebo mean change from Baseline in SF-36 PCS at Week 24 of 2.08, SD 9.51 (N=63). With those assumptions, the study has >99% power to detect a true treatment difference of 5.83 at the planned sample size.

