**Table 14–1: Treatment effect by elevated hs-CRP and/or bone erosion at Baseline for secondary efficacy analyses**

Subjects with elevated hs-CRP and/or bone erosion at Baseline	Treatment difference/standard deviation	
	Treatment effect = -0.3 SD=0.72 vs 0.71	Treatment effect = -0.35 SD=0.81 vs 0.93
20%	67	62
25%	76	72
30%	84	79
35%	89	85
40%	92	89
45%	95	92
50%	96	95

hs-CRP=high sensitivity C-reactive protein; SD=standard deviation

For enthesis free-state at Week 16, enthesis resolution data from the FUTURE 5 study at Week 16 were used to estimate the bimekizumab 160mg Q4W treatment and placebo groups. In FUTURE 5 The treatment effect estimate from the secukinumab 150mg treatment group at Week 16 was 55% (n=141) and the placebo group estimate was 36% (n=192). Assuming a BKZ response of 55% and a placebo rate of 39% and having 25% of subjects with Baseline enthesis the pooled PA0010/PA0011 the studies have a 69% power to detect a true treatment difference of 16% (odds ratio 1.91).

For dactylitis-free state at Week 16, dactylitis resolution data of the FUTURE 5 study (Mease et al, 2018) at Week 16 were used to estimate the bimekizumab 160mg Q4W treatment and placebo groups. The treatment effect estimate from the secukinumab 150mg treatment group at Week 16 of 56% (n=103) is assumed versus a placebo group estimate of 32% (n=124). With those assumptions and having 11% of subjects with Baseline dactylitis, the pooled PA0010/PA0011 studies have a 66% power to detect a true treatment difference of 24% (odds ratio 2.71).

Treatment difference in change from Baseline in vdHmTSS at Week 16 in the overall population is estimated using the data from the FUTURE 5 study in a mixed TNF $\alpha$  exposure population. The bimekizumab 160mg Q4W group treatment difference compared to placebo is estimated to be the same as the difference in change from Baseline in vdHmTSS at Week 16 between the secukinumab 150mg group and placebo which is 0.42, assuming a SD of 1.13 for bimekizumab and SD=2.44 for placebo. With these assumptions the study has 76% power to detect a treatment difference of 0.42 in the planned sample size.

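### The logistic model for enthesitis-free state at Week 16 omits Baseline LEI and so forgoes precision that would cost nothing

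*Protocol*

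**What the plan says.** - **Endpoint.** Section 4.2.1: "Enthesitis-free state in the Leeds Enthesitis Index (LEI) at Week 16 in the subgroup of subjects with enthesitis at Baseline", in the pooled PA0010 and PA0011 population. Section 14.3.1.2 includes it among the binary variables of the testing hierarchy.
- **Scale.** Section 9.14 describes three sites on each side, palpated "bilaterally and scored as 0=no pain and 1=painful", so the score runs from 0 to 6.
- **Model.** Section 14.3.1.2: "The binary variables will be analyzed using the same analysis methods and estimand approach as used for the primary variable". For the primary variable, Section 14.3.1.1 says "The model will include a fixed effect for treatment"; region and bone erosion are added if found suitable. No Baseline disease score is named.
- **Contrast.** The continuous hierarchy endpoints in Section 14.3.1.2 (HAQ-DI, SF-36 PCS, vdHmTSS) are analysed by ANCOVA with the Baseline value as covariate.
- **Power.** Section 14.9.2: "Assuming a BKZ response of 55% and a placebo rate of 39% and having 25% of subjects with Baseline enthesis", the pooled studies have 69% power.
- **Consequence of failure.** Section 14.3.1 stops the fixed sequence at the first hypothesis that is not rejected.

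**The concern.** The endpoint requires every site to be clear. A subject who enters with one tender site needs one site to resolve; a subject with six needs all six. If sites cleared independently with probability c, the chance of response would be c for the first subject and c^6 for the second. Some association between Baseline LEI and response is therefore to be expected from how the endpoint is built, although its strength is not documented.

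Leaving such a covariate out of a logistic model does not invalidate the test under randomization. It does leave prognostic variation unexplained, so the same data give a less powerful test. That matters more here than for endpoints with over 99% power: the stated figure is 69%, and a failed test ends the sequence. In the order of Section 4.2.1, dactylitis-free state (66% stated power) and overall vdHmTSS (76%) follow it.

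Section 14.3.1.2 already tailors covariates to the endpoint, since it removes bone erosion for skin outcomes. An enthesitis-specific term would fit the same approach.

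**Working it through.** **Step 1. Reproduce the stated 69%.**

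Inputs:
- Section 14.9: "All sample size and power calculations were done at a significance level of 0.05".
- Section 14.9.2: "All power calculations for binary endpoints were performed using a 2-sided 2-sample Chi-square test with continuity correction".
- Rates of 55% and 39%, with 25% of subjects having Baseline enthesitis (Section 14.9.2).
- PA0010 arms of 420 and 280 (Section 14.9), so 105 and 70 with enthesitis.
- PA0011 size: not given in the protocol. Assumed to be 400 subjects in the two arms at 2:1, found by solving back from the stated power. Pooled arms are then 687 and 413, giving n1 = 0.25 × 687 = 171.75 and n2 = 0.25 × 413 = 103.25.

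Formula: power = Φ{[d − ½(1/n1 + 1/n2) − 1.96·SE0] / SE1}

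- Pooled rate = (171.75 × 0.55 + 103.25 × 0.39) / 275 = 0.490
- SE0 = √[0.490 × 0.510 × (1/171.75 + 1/103.25)] = 0.0623
- SE1 = √[0.55 × 0.45/171.75 + 0.39 × 0.61/103.25] = 0.0612
- Continuity correction = 0.0078
- Power = Φ[(0.16 − 0.0078 − 0.1220)/0.0612] = Φ(0.494) = **68.9%**, against 69% stated

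Cross-checks:
- The odds ratio is (0.55/0.45)/(0.39/0.61) = 1.91, as stated.
- On the same pooled size, 11% with dactylitis and 56% against 32% give 66.7%, against 66% stated.
- Without the continuity correction the enthesitis power is 73.3%. This is the figure comparable with an unadjusted Wald test.

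**Step 2. Effect of adding Baseline LEI.**

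Simulation model: logit P(response) = a(arm) − s × (Baseline LEI − 1), where s is the fall in log-odds per extra Baseline site. The two intercepts are solved so that the marginal rates stay at 55% and 39%. Treatment is tested by a 2-sided Wald test at 0.05, with and without Baseline LEI in the model.

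Assumed: 165 and 100 subjects, and a Baseline LEI mix for scores 1 to 6 of 27/28/15/14/6/10%. These arm sizes imply 60 and 30 PA0011 subjects with enthesitis (165 − 105 and 100 − 70), slightly fewer than in Step 1.

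| s per site (odds factor) | Unadjusted | With Baseline LEI | Gain |
|---|---|---|---|
| 0 (1.0) | 72% | 72% | 0 |
| 0.26 (1.3) | 73% | 74% | about 1 |
| 0.41 (1.5) | 72% | 76% | about 4 |
| 0.59 (1.8) | 72% | 79% | about 7 |

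Type I error was near 5% either way.

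**Step 3. Sensitivity to the assumed LEI mix.**

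With 172 and 103 subjects, 3,000 runs per cell and two other mixes (25% or 45% one-site subjects), the results were:

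- s = 0: no gain.
- s = 0.2: about 1 point.
- s = 0.4: 3 to 4 points (for example 73.2% to 76.9%, and 72.1% to 75.1%).
- s = 0.6: 6 to 8 points (72.8% to 78.6%, and 72.1% to 80.3%).
- s = 0.8, a steeper slope: 7 to 12 points (74.2% to 81.3%, and 72.9% to 84.9%).

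Simulation error on each power figure is about √(0.72 × 0.28/3000) = 0.8 points.

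**The case against.** The strongest reply is that this is a design preference. Section 14 leaves detail to the SAP, and even region and bone erosion are subject to a suitability assessment. The binary endpoints follow the primary model consistently, and ANCOVA on change scores routinely takes the Baseline value. Change from Baseline in LEI is also kept as an other efficacy variable (Section 4.3.1). Much of this stands: there is no contradiction in the protocol and no threat to validity. But the protocol does name the terms of this model and applies them to a confirmatory test, so a recommendation about those terms is in order.

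The size of the gain is also open to challenge, and rightly so. The protocol gives no Baseline LEI distribution, no association between Baseline LEI and clearance, and no PA0011 size. The adjusted 79% must not be set beside the stated 69%, because the latter includes a continuity correction. The like-for-like comparison is 72% with 79%.

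Two stronger readings are tempting:

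- *Examination noise in one-site subjects pulls power below 69%.* Entry and response each rest on a single examination, so a reader might infer this. It would follow only if 55% and 39% were noise-free. Symmetric errors of 3%, 5% or 10% would then give 63%, 59% or 49%. But the rates derive from resolution observed in another trial (55% and 36%, with placebo raised to 39%), so ordinary noise is probably already in them. A Baseline covariate would not correct misclassification in any case.
- *Baseline LEI is the main predictor of response.* The endpoint's construction makes an association likely, but nothing in the protocol shows its strength.

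The cut-offs themselves (LEI of at least 1 to enter, LEI of 0 to respond) are the natural reading, but are not written out.

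**Conclusion.** The point holds as a missed gain in efficiency. The stated model for enthesitis-free state omits a Baseline score that is already collected and probably prognostic, in a sequence that stops at failure and at a step with 69% stated power. The 69% reproduces under an assumed PA0011 size and is not wrong; the test is valid with or without the covariate.

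The forgone power is about 0 to 7 points on the Wald test for an assumed fall of 0 to 0.6 in log-odds of response per Baseline site. It is nil if Baseline LEI is not prognostic and larger only under steeper slopes than that. No scenario run showed a meaningful loss from adjusting. These figures rest on the assumed PA0011 size, LEI distribution and linear effect of LEI on the log-odds, so no single power loss should be asserted.

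The stated summary measure is already a conditional odds ratio, so its type does not change. Its value does: with marginal rates of 55% and 39%, the odds ratio conditional on LEI is about 2.0 at s = 0.4 and 2.1 to 2.2 at s = 0.6, against 1.91 unadjusted.

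**What to change.** In Section 14.3.1.2, and correspondingly in the SAP, before treatment codes are released for the Week 24 analysis:

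1. Prespecify the Baseline LEI score as a covariate in the logistic model for enthesitis-free state, with treatment and whichever of region and bone erosion are retained.
2. By the same reasoning, prespecify a Baseline dactylitis measure for dactylitis-free state. No separate calculation was run for this endpoint. On the Step 1 sizes it has only about 76 and 45 subjects (0.11 × 687 and 0.11 × 413), so a single linear term is preferable.
3. Optionally, add a supportive summary of enthesitis-free state by Baseline LEI (1 against 2 or more), to show how far single-site changes drive the result. This addresses what the covariate cannot.

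The cost is one or two sentences and one degree of freedom per model. LEI and LDI are already recorded at Baseline, and everyone in the enthesitis subgroup is there because of a Baseline LEI assessment. No extra patients or visits are needed.
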